Application of Ideal Binary Masking to Disordered Speech

NCT05244603

12/3/2019

Study Protocol

Dysarthria and hearing loss are communication disorders that can substantially reduce intelligibility of speech and the addition of background noise adds a further challenge. This proposal utilizes an established signal processing technique, currently exploited for improved understanding of speech in noise for listeners with hearing loss, to investigate its potential application to overcome speech-in-noise difficulties for listeners understanding dysarthric speech. Successful completion of this project will demonstrate proof-of-concept for the application of this signal processing technique to dysarthric speech in noise, and inform the development of an R01 proposal to perform a large-scale evaluation of the technology, and clinically meaningful implications, in a broad range of disordered speech types and severities.

Dysarthric and healthy control phrases will be processed in six different experimental conditions. Conditions 1 and 2 will consist of the unprocessed phrases representing dysarthric (condition 1) and control speech (condition 2) in quiet. Conditions 3 and 4 will consist of the phrases representing dysarthric (condition 3) and control speech (condition 4) mixed with noise at a given signal-to-noise ratio (SNR). For a masker, a cafeteria noise (Auditec of St. Louis) will be used to represent a relatively natural listening background. Conditions 5 and 6 will consist of the same phrases representing dysarthric (condition 5) and control speech (condition 6) mixed with cafeteria noise as in conditions 3 and 4, but processed by the IBM. Speech stimuli will be processed by custom MATLAB scripts and will be generated using high-quality D/A converters and a PC.

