The outcome measure for the current study is percent words correct (PWC). To test whether there is a difference in PWC between the experimental conditions, linear mixed effects regression analysis will be used. Each mixed effects model will control for covariates including individual age, gender, MOCA score, audiometric thresholds, frequency-specific audibility of stimuli, and QuickSIN scores. We will also assess PWC scores in quiet as both a covariate and as a potential moderator—thereby controlling for baseline perception capabilities—and intra-individual variability. Of particular interest is whether the IBM-processed speech is significantly more intelligible than unprocessed speech in noise (which would indicate that IBM processing provides benefit). These models will also test whether IBM-processed speech is not significantly different from unprocessed speech in quiet (which would provide evidence that IBM processing restores intelligibility of speech in noise to that of speech in quiet). These tests will be done systematically. The first aim includes the unadjusted (bivariate) model as well as the adjusted model discussed in the Research Strategy. Aim 2 builds on this by including important moderators.

For power, we used the *simr* R package to simulate power given the sample size and expected effect sizes. This analysis relied on Monte Carlo simulations from a known population model. All code used is provided below. For Aim 1, a minimum of 30 participants will be tested per sub-experiment, as this results in sufficient power for the planned comparisons (for alpha of .05, with 6 covariates, effect size of .5, power = .93).

For Aim 2, at least 30 participants will be tested, as the power analyses with a moderate interactive effect indicate this sample size will result in sufficient power for the planned interactions (for alpha of .05, with 6 covariates, power = .91).

The R code to run the analyses are provided below.

```
library(tidyverse)
set.seed(843)

library(simr)

data_production <- function(npart = 30,          ## number of subjects
                           nplot = 6,          ## number of repeated measures
                           effect_x = .5,      ## effect of variable x
                           sigma_s = 2,         ## variance within participant
                           sigma = 1) {         ## residual variance

  x = rep(1:nplot, times = nplot)
  z = rnorm(npart*nplot)
  a = rnorm(npart*nplot)
  b = rnorm(npart*nplot)

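### Restoration to quiet can be concluded from IBM versus quiet alone, without requiring that IBM beat unprocessed speech in noise

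*Combined protocol and SAP*

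**What the plan says.** The combined protocol and SAP, under Statistical Design and Power, attaches two conclusions to the same mixed models of percent words correct (PWC).

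- **Benefit.** "Of particular interest is whether the IBM-processed speech is significantly more intelligible than unprocessed speech in noise". A significant result is read as benefit.
- **Restoration.** "These models will also test whether IBM-processed speech is not significantly different from unprocessed speech in quiet". A non-significant result is read as one "which would provide evidence that IBM processing restores intelligibility of speech in noise to that of speech in quiet".

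The only sentence that bears on how the two tests relate is "These tests will be done systematically". It sets neither an order nor a condition.

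The Study Protocol section defines six conditions: quiet (1 dysarthric, 2 control), noise (3, 4) and noise processed by IBM (5, 6). It gives no value for the signal-to-noise ratio and no expected fall in PWC from quiet to noise. The sample size is that "a minimum of 30 participants will be tested per sub-experiment", with Aim 1 power stated as "for alpha of .05, with 6 covariates, effect size of .5, power = .93".

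**The concern.** To restore something means that it was lost and then recovered. The restoration criterion takes two inputs, IBM (5, 6) and quiet (1, 2). The noise score (3, 4) is not one of them, and the benefit result is not a precondition. If IBM does nothing, its mean equals the noise mean, and the criterion is met whenever the noise deficit is too small to detect. The conclusion is then easiest to reach where noise mattered least.

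At stake is one of the two conclusions the models are meant to support, in a proof-of-concept study intended to inform a larger proposal. A report could credit IBM with restoration in a speech type where it had no effect.

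**Working it through.** **The plan's own figure.** Regenerating the data with the listed code and seed 843 gives a residual SD of 0.4076 and a participant SD of 0.888. With the coded effects 0.15, 0.15, 0.30, 0.30 and 0.45 and 2,500 simulated data sets, the 5-df omnibus test of condition has power 0.944 (F test) or 0.955 (likelihood ratio). The stated figure is .93. The simulation was hand-coded in place of the simr package, and the number of runs behind .93 is not given. I take the F result as an adequate reproduction. It concerns the omnibus test, not the IBM-versus-quiet contrast.

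**Inputs for the restoration criterion.**
- n = 30 (Statistical Design and Power).
- Alpha .05, taken as two-sided (sidedness is not stated).
- One score per listener and condition, random-intercept model (as in the code).
- Residual SD. The code has participant variance 2² = 4, residual variance 1 and condition effect 0.5x with x = 1 to 6. The variance of x is 35/12 = 2.917, so the condition part is 0.25 × 2.917 = 0.73. The total is 0.73 + 4 + 1 = 5.73. After scaling, the residual SD is 1/√5.73 = 0.418.
- Noise deficit d (quiet minus noise): not in the documents, so it is varied.

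**Formula.** The SE of a two-condition contrast is 0.418 × √(2/30) = 0.108. Residual df are 29 × 5 = 145, with critical t = 1.976. If IBM has no effect, the IBM-versus-quiet difference is d, and the chance of non-significance is P(|T| < 1.976), where T is noncentral t with 145 df and noncentrality d/0.108.

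| Deficit d | d/SE | Zero-effect IBM meets the criterion |
|---|---|---|
| 0 | 0 | 95% |
| 0.10 | 0.93 | 85% |
| 0.15 | 1.39 | 72% |
| 0.20 | 1.85 | 55% |
| 0.30 | 2.78 | 21% |
| 0.45 | 4.17 | 1.4% |

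A fully restoring IBM meets the criterion 95% of the time at every d. For residual SDs from 0.36 to 0.47, the value at d = 0.15 runs from 64% to 77%. With the six covariates in the seed-843 fit it is 72% at 0.15 and 22% at 0.30.

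**Would an equivalence margin be enough?** Take an illustrative margin of 0.30 (my assumption) and two one-sided 5% tests. A zero-effect IBM still passes 74%, 69% and 56% of the time at d = 0, 0.05 and 0.10. A margin alone does not remove the problem when the deficit lies inside it.

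**Adding the plan's own benefit test.** If IBM does nothing, it is significantly above noise with probability at most 0.05/2 = 2.5%, whatever d is. That bounds the joint error. I simulated three independent condition means with SD 0.418/√30 and a pooled residual on 145 df. The joint error was 2.0% at d = 0, at most 2.4% at any d tried, and 1.6% at 0.30.

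| Full restoration recognised | d = 0.30 | d = 0.45 |
|---|---|---|
| Criterion as written | 95% | 95% |
| Plus IBM > noise | 76% | 94% |
| Plus IBM > noise and noise < quiet | 66% | 93% |

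The third row buys little, because the second already controls the zero-effect error.

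**The case against.** The strongest reply is that the benefit test is in the preceding sentence and is the one the plan marks as of particular interest. A useless IBM would normally be reported as showing no benefit, from the same models. The plan also says only that non-significance would be evidence, in a proof-of-concept study. This stands as mitigation. It still leaves a report free to state no benefit and restoration side by side, with no rule for reconciling them.

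Several stronger readings are tempting, and the documents do not support them:
- **That noise is never compared with quiet.** The planned model covers differences across all six conditions, so 3 v 1 and 4 v 2 can be estimated from it. They are just not named.
- **That the chosen noise level will barely affect control speech.** Nothing says so. The text does not even say that both speech types share one signal-to-noise ratio, and it describes noise as a further difficulty.
- **That 0.15 to 0.45 are the expected noise deficits.** They are coefficients of levels 2 to 6 against level 1 and carry no such label. If levels follow condition numbers, condition 3 (noise) sits 0.15 above condition 1 (quiet), so they cannot be deficits. I use them only to mark the scale.

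Two further points stand in part. The plan refers to a Research Strategy that is not among the documents, and an order of tests may be set there. And at deficits of about 0.10 to 0.30, part of the misfiring reflects the separate weakness of reading non-significance as equality. The missing link matters in its own right mainly where the deficit is near zero or inside any reasonable margin.

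**Conclusion.** The point holds in limited form. As written, restoration can be concluded without evidence that IBM did anything. For a zero-effect IBM the chance is about 95% at no deficit, 72% at 0.15, 21% at 0.30 and 1.4% at 0.45. These figures assume n = 30, one score per listener and condition, residual SD 0.418 on the scaled outcome and two-sided alpha .05.

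A reader might infer that the study will credit IBM falsely. That does not follow. The true deficit is unknown, the problem all but disappears if noise does substantial damage, and the benefit result will be available alongside. This is a stated rule that can give a wrong conclusion. It is worth correcting, and it does not undermine the benefit comparison.

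**What to change.** In Statistical Design and Power, state that restoration is claimed, separately for each speech type, only if both of these hold:
1. IBM PWC is significantly above unprocessed-noise PWC (5 v 3; 6 v 4).
2. The IBM-versus-quiet criterion is met (5 v 1; 6 v 2).

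Beside any such claim, report the estimated noise-versus-quiet difference (3 v 1; 4 v 2) with its 95% CI from the same model, so that readers can see whether there was a loss to restore. It need not be a further significance gate. At a deficit of 0.30 that would cut recognition of full restoration from about 76% to 66% for little gain.

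**Cost.** One or two sentences and contrasts from the model already planned, with no new data or participants. The claim becomes harder to earn at modest deficits: full restoration is recognised about 76% of the time at 0.30 and 94% at 0.45, instead of 95%.

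**What it leaves open.** The change does not cure reading non-significance as equality. In the same simulation, an IBM that recovers half the deficit is still called restoring about 25% of the time at 0.30 and 33% at 0.45. That needs its own remedy.

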  c = rnorm(npart*nplot)
  d = rnorm(npart*nplot)
  e = rnorm(npart*nplot)
  f = rnorm(npart*nplot)
  standeff = rep( rnorm(npart, 0, sigma_s), each = nplot)
  stand = as.character(rep(1:npart, each = nplot))
  ploteff = rnorm(npart*nplot, 0, sigma)
  resp = 1 + effect_x*x + standeff + ploteff
  dat = data.frame(x = as.character(x), z = scale(z), stand, resp = scale(resp), a, b, c, d, e, f)
  dat
}

data_production_int <- function(npart = 30,          ## number of subjects
                                 nplot = 6,          ## number of repeated measures
                                 effect_x = .5,      ## effect of variable x
                                 sigma_s = 2,         ## variance within participant
                                 sigma = 1) {         ## residual variance

  x = rep(1:nplot, times = nplot)
  z = rnorm(npart*nplot)
  a = rnorm(npart*nplot)
  b = rnorm(npart*nplot)
  c = rnorm(npart*nplot)
  d = rnorm(npart*nplot)
  e = rnorm(npart*nplot)
  f = rnorm(npart*nplot)
  standeff = rep( rnorm(npart, 0, sigma_s), each = nplot)
  stand = as.character(rep(1:npart, each = nplot))
  ploteff = rnorm(npart*nplot, 0, sigma)
  resp = 1 + effect_x*x + effect_x*x*z + effect_x*x*x*z + standeff + ploteff
  dat = data.frame(x = as.character(x), z = scale(z), stand, resp = scale(resp), a, b, c, d, e, f)
```

```

dat
}

d <- data_production()
fit <- lmer(resp ~ x + a + b + c + d + e + f + (1|stand), data = d)
fit2 <- extend(fit, along="stand", n=30)
fixef(fit2)[2:3] <- 0.15
fixef(fit2)[4:5] <- 0.30
fixef(fit2)[6] <- 0.45

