# summary(fit2)

broom:::augment(fit2) %>%
  ggplot(aes(factor(x), .fitted, fill = factor(x), color = factor(x))) +
  geom_boxplot(alpha = .7) +
  theme_classic() +
  scale_fill_viridis_d() +
  scale_color_viridis_d() +
  theme(legend.position = "none")

sim1 <- powerSim(fit2)
sim1

d2 <- data_production_int()
fit <- lmer(resp ~ x*z + a + b + c + d + e + f + (1|stand), data = d2)
fit2 <- extend(fit, along="stand", n=30)
fixef(fit2)[14] <- 0.2
fixef(fit2)[15] <- 0.2
fixef(fit2)[16] <- 0.3
fixef(fit2)[17] <- 0.3
fixef(fit2)[18] <- 0.4

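### The Aim 1 power of .93 is not for an effect of .5 and not for IBM versus noise; it fits an omnibus test of condition at coefficients of 0.15 to 0.45

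*Combined protocol and SAP*

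**What the plan says.** The section Statistical Design and Power opens with a general question, "To test whether there is a difference in PWC between the experimental conditions", and then narrows it: "Of particular interest is whether the IBM-processed speech is significantly more intelligible than unprocessed speech in noise". It also plans to compare IBM-processed speech with speech in quiet and to read a non-significant result as a finding "which would provide evidence that IBM processing restores intelligibility of speech in noise to that of speech in quiet".

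The Aim 1 sample size is at least 30 listeners per sub-experiment, "as this results in sufficient power for the planned comparisons (for alpha of .05, with 6 covariates, effect size of .5, power = .93"). The plan states that all the code behind the figure is supplied, so the code is the full basis of the claim.

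In that code the condition coefficients are reset after the model is fitted, from "fixef(fit2)[2:3] <- 0.15" up to "fixef(fit2)[6] <- 0.45". Aim 1 power then comes from a single call, "sim1 <- powerSim(fit2"), with no further argument. The only other power call is the Aim 2 interaction test.

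The Study Protocol defines the conditions. Conditions 1 and 2 are quiet (dysarthric, control). "Conditions 3 and 4 will consist of the phrases representing dysarthric (condition 3) and control speech (condition 4) mixed with noise". Conditions 5 and 6 are the IBM-processed versions.

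**The concern.** The sentence that justifies the sample size ties .93 to an effect of .5 and to the planned comparisons. The code supports neither. No coefficient it evaluates equals .5, no two levels differ by .5, and no contrast of conditions 5 and 6 with 3 and 4 is tested.

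The .93 is the only reason given for 30 listeners in Aim 1. Power for a joint test of six levels does not depend on which level carries which label. It is therefore not the power to detect an IBM benefit, and a reader who takes it as such has no basis for judging whether 30 is enough for the main question.

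**Working it through.** **Inputs, all from the posted code.** 30 participants, 6 levels, `effect_x` = .5, participant SD 2 and residual SD 1 (both passed to `rnorm` as SDs), response scaled to total SD 1, random intercept, six covariates, alpha .05. After overwriting, the level effects are 0, 0.15, 0.15, 0.30, 0.30 and 0.45. Contrasts below are taken as two-sided, which the plan does not state.

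**1. Residual SD after scaling.** The variance of 1 to 6 is 35/12 = 2.917. Expected total variance = .25 × 2.917 + 4 + 1 = 5.729, so the total SD is 2.394 and the residual SD is 1/2.394 = 0.418. Running the posted data step in R with seed 843 gives a residual SD of 0.408 and an intercept SD of 0.888.

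**2. Reproducing .93.** The mean level effect is 1.35/6 = 0.225. The sum of squared deviations is 2 × 0.225² + 4 × 0.075² = 0.12375. The omnibus noncentrality is 30 × 0.12375/0.418² ≈ 21.3, giving power of about .96 if covariate overlap is ignored. With the six covariates as generated under seed 843, the noncentral F gives .934 (residual SD 0.418) to .946 (0.408). The median over 400 regenerated datasets is .933. Simulating and refitting 1,000 times, in place of simr, gives .94 to .95 by F and .95 to .96 by likelihood ratio. So .93 fits the omnibus test at the overwritten coefficients.

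**3. Readings of .5 do not give .93.** One pair differing by .5 total SD gives .995. One pair differing by .5 residual SD gives .46. A slope of .5 per step, tested jointly, gives above .999. Two steps of .5 on the unscaled response give .96. A paired t test with d = .5 and n = 30 gives .75.

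**4. Power formula for IBM versus noise.** The random intercept cancels within listener. For one speech type, SE = σ√(2/30). For the average of both types, SE = σ√(1/30). With σ = 0.408 to 0.418, SE is 0.105 to 0.108 per type and 0.074 to 0.076 pooled. For a difference of 0.15 the ratio to SE is 1.39 to 1.42 per type and 1.97 to 2.01 pooled. Noncentral t with 139 df then gives .28 to .29 and .50 to .52. The ranges below also include the simulated values.

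**5. Effect of the missing mapping.** Six values with two tied pairs can be assigned to six conditions in 6!/(2!·2!) = 180 distinct ways.

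| Assignment | IBM − noise, by type | Power per type | Power pooled |
|---|---|---|---|
| Levels 1–6 = conditions 1–6 (puts quiet below noise) | 0.15 and 0.15 | .26–.29 | .48–.52 |
| Noise ≤ IBM ≤ quiet, IBM strictly above noise in both types (4 of 180) | 0.15 and 0.15 | .26–.29 | .45–.52 |
| Same ordering, benefit in one type only (4 of 180) | 0.30 and 0 | .74–.81 in that type | .45–.52 |
| Same ordering, benefit in one type only (2 of 180) | 0.15 and 0 | .26–.29 in that type | .16–.17 |
| Noise 0 and 0.15, IBM 0.30 and 0.45 | 0.30 and 0.30 | .74–.81 | .97–.98 |

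All 24 assignments with a pooled difference above 0.15 place IBM above quiet in at least one speech type. A difference of 0.45 (power .98 to .99) is possible in one type but never in both, so under no assignment do both per-type contrasts reach .93.

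**6. Label invariance.** The omnibus power is the same for the 4 assignments with IBM equal to noise in both types, and for the 34 with IBM below noise in both, as for any assignment with a benefit.

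**7. Secondary point.** The code comments call 2 and 1 variances. If variances were meant, the total variance is .729 + 2 + 1 = 3.729, the residual SD is 1/1.931 = 0.518, and omnibus power is about .82.

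**The case against.** The strongest reply is that no sum is wrong: the .93 reproduces, and an omnibus test answers the plan's opening question. That stands. The fault is that the figure is attached to the wrong effect and the wrong comparison.

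A second reply is that the contrast power depends wholly on an unstated mapping, so low values prove nothing about the study. This also stands in part. Some assignments give high power: up to .98 pooled, about .74 to .81 for one type within the plausible ordering (in two of those four assignments the type is dysarthric speech, the focus of the project), and .98 to .99 for a single type at 0.45. The low values describe the posted coefficients, not the true IBM benefit. But a range of .16 to .98 is itself the problem: the stated .93 does not settle it.

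Third, simr was not run and its default test is inferred from the call and the numerical match, hence consistent with. That no coefficient is .5 and that no such contrast is coded can be seen by reading the code.

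Fourth, the plan refers to a Research Strategy that is not among the documents and may say whether speech types are pooled. If so, that part needs only a cross-reference. It would not supply the missing power calculation.

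Finally, this is a proof-of-concept study and 30 is a floor. That limits the consequences but does not make the sentence correct.

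**Conclusion.** The concern holds. As written, the Aim 1 power statement is wrong about its effect size and about what it covers. The .93 is consistent with an omnibus test of condition at 0.15/0.15/0.30/0.30/0.45 of the scaled response. Power for IBM versus noise at 30 listeners has not been computed and cannot be recovered from the documents. Whether the study is adequately powered for that contrast is open. The illustrative powers assume two-sided tests at .05, the code's variance structure and the mappings shown. Because .93 is the sole support for the Aim 1 sample size, it should be corrected before anyone relies on it.

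**What to change.** 1. Describe .93 as the omnibus test of condition at the overwritten coefficients, after confirming which test the call ran, and delete the effect size of .5.
2. Map the six code levels to the six conditions and justify the assumed ordering.
3. State whether IBM versus noise is tested per speech type, pooled, or both.
4. Rerun the simulation for that contrast and report its power. Alternatively, report the detectable difference at 30 listeners, in SD of the scaled response. With the six covariates allowed for, this is about 0.30 to 0.31 at 80% power and 0.37 to 0.38 at 93% per speech type, and about 0.21 to 0.22 and 0.26 to 0.27 pooled.
5. Reconcile the variance comments with the SDs the code uses.

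The cost is one rerun and a restated figure. The change itself adds no participants. The restated power may be less favourable, depending on the mapping and pooling chosen.

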# summary(fit2)

broom:::augment(fit2) %>%
  ggplot(aes(z, .fitted, fill = factor(x), color = factor(x))) +
  geom_point(alpha = .7) +
  geom_smooth(method = "lm") +
  theme_classic() +
  scale_fill_viridis_d() +
  scale_color_viridis_d()

sim2 <- powerSim(fit2, test = fcompare(~ x + z))
sim2

```

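### The printed Aim 2 power code gives about 1.00, not the stated .91, and its null model drops the six covariates along with the interaction

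*Combined protocol and SAP*

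**What the plan says.** The Statistical Design and Power section fixes the Aim 2 sample size by simulation: "For Aim 2, at least 30 participants will be tested". The reason it gives is that "power analyses with a moderate interactive effect indicate this sample size will result in sufficient power for the planned interactions". The settings and result attached to that claim are stated as "for alpha of .05, with 6 covariates, power = .91". The section adds that "All code used is provided below".

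The Aim 2 part of that code does four things:

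- It generates the response as "resp = 1 + effect_x*x + effect_x*x*z + effect_x*x*x*z + standeff + ploteff", with `effect_x` = .5, and standardises it with `scale(resp)` before returning the data.
- It fits the full model: "fit <- lmer(resp ~ x*z + a + b + c + d + e + f + (1|stand), data = d2".
- It overwrites fixed effects 14 to 18 with 0.2, 0.2, 0.3, 0.3 and 0.4, the last by "fixef(fit2)[18] <- 0.4".
- It estimates power by comparing the full model with a smaller one: "sim2 <- powerSim(fit2, test = fcompare(~ x + z".

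**The concern.** The .91 is the only stated basis for 30 participants in Aim 2. A reader who is told that the code is complete should be able to run it, recover the figure, and learn what effect size and noise level it stands for.

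Two features of the code prevent this. First, the interaction coefficients are imposed on a scale that the generator's own large interaction has already shrunk, so they are far bigger relative to the noise than they look. Second, the reduced model has only x and z as fixed effects. It therefore removes the covariates a to f together with the interaction, although the text reports power for the interactions with six covariates in the model.

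**Working it through.** **Inputs, all from the printed code.** 30 participants × 6 measures = 180 rows. The between-participant SD is 2 and the residual SD is 1 before scaling (the comments call these variances, but `rnorm` uses them as SDs). `effect_x` = .5; alpha .05. The fixed effects run: intercept (1), five x terms (2–6), z (7), a to f (8–13), five x-by-z terms (14–18). Positions 14–18 are therefore the interaction, as intended.

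**Residual SD after scaling, Aim 2.** The slope on z at level x is 0.5(x + x²), that is 1, 3, 6, 10, 15, 21.

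- Mean squared slope: (1 + 9 + 36 + 100 + 225 + 441)/6 = 135.33.
- Variance of 0.5x over x = 1 to 6: 0.25 × 2.917 = 0.73.
- Total variance: 135.33 + 0.73 + 4 + 1 = 141.06, so the SD is 11.88.
- Scaled residual SD: 1/11.88 = 0.084. Over 2,000 generated datasets the mean was 0.085 (95% range 0.073 to 0.099).
- Imposed coefficients in residual SDs: 0.2/0.085 = 2.4 up to 0.4/0.085 = 4.7.

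**The same quantity for Aim 1.** Variance 4 + 1 + 0.73 = 5.73 and SD 2.39, so the scaled residual SD is 1/2.39 = 0.418 and the participant SD is 2/2.39 = 0.836. On that scale the same coefficients would be 0.2/0.418 = 0.48 to 0.4/0.418 = 0.96 residual SDs.

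**Attempt to reproduce the stated figures.** The `simr` package was not available, so its steps were coded directly: fit the generated data, keep the fitted variances, overwrite the coefficients, simulate, refit both models by maximum likelihood, and take the likelihood-ratio test. As a check on the method, this routine gives .938 on average for Aim 1, against the stated .93. For Aim 2 it does not give .91:

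| Set-up (60 datasets × 300 replicates) | Printed null, 11 df | Covariates kept in null, 5 df |
|---|---|---|
| As printed | 1.00 | 1.00 |
| Interaction zero, covariates at chance-fitted values | .367 (.113–.840 by dataset) | .077 |
| Interaction zero, covariate effects also zero | .083 | .079 |
| Printed coefficients, Aim 1 noise, covariate effects zero | .699 | .818 (.67–.94 by dataset) |

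A separate Python implementation of the printed set-up rejected in 2,000 of 2,000 simulations. `lme4` rejected in 200 of 200 for each of two seeds, with a largest p-value of about 5e-21.

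**Noise level that would give .91.** With the printed coefficients, the 11-df test has power .926 at a residual SD of 0.32 and .879 at 0.34. The 5-df test has .914 at 0.36 and .889 at 0.38. So .91 needs a residual SD of about 0.33 (11 df) or 0.36 (5 df), roughly four times the 0.085 in the code.

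**Degrees of freedom.** The full model has 18 fixed effects. The reduced model has 1 + 5 + 1 = 7. The difference is 11: five interaction terms and six covariates.

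**The case against.** - **Cause.** Standardising cannot be the whole explanation, because Aim 1 also standardises and its power is recovered. This is right: the 1.00 comes from standardising after a very large generated interaction and then imposing coefficients on the standardised scale. The null model is ruled out as the cause, since both nulls give 1.00.
- **The 37% rejection rate.** It is not a false-positive rate. The covariates carry non-zero fitted coefficients there, so the joint null is false and rejecting it is correct. That stands: the figure shows only that rejection is not specific to the interaction. The reduced model also appears only in the planning simulation; the text does not make it the Aim 2 analysis test.
- **The .82.** It is illustrative. Separate runs under Aim 1's noise gave .78 to .82 for the 5-df test. The code draws the moderator afresh on every row, whereas a baseline score in quiet would be more natural as one value per listener; with one value per participant, power was about .89. The likelihood-ratio test itself rejects about 8% of the time at a nominal 5%, so these powers are slightly optimistic.
- **Consequence.** The code errs towards more power than stated, the sample size is a minimum, and the study is proof-of-concept. This limits the seriousness, but the 1.00 is no reassurance: with the response left unscaled (residual SD about 1) and the same coefficients, interaction-only power is about .22.
- **Reproduction.** `simr` was not run, and the random state when the Aim 2 data are drawn depends on the preceding Aim 1 simulation. With p-values this small and no dataset departing from 1.00, neither point could plausibly bring the result down to .91. A different version of the code may have produced the .91, but that is conjecture.

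**Conclusion.** The concern holds. The printed Aim 2 code gives power of about 1.00, not .91, because its effects are about 2.4 to 4.7 residual SDs instead of moderate. Its comparison is an 11-df joint test of interaction and covariates instead of the 5-df interaction test that the text describes. These are separate defects.

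The first conclusion rests on the code as printed and on a direct recoding of the simulate-and-refit step; it did not vary over the datasets generated. The finding does not show that 30 participants are too few. It shows that the stated justification cannot be traced to its source, and that the power depends almost entirely on a noise level the plan does not state. It should be corrected, but it does not call the design into question.

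**What to change.** 1. Keep the covariates in the reduced model: `fcompare(~ x + z + a + b + c + d + e + f)`.
2. Set the residual and participant variances explicitly to match Aim 1 (SDs of about 0.418 and 0.836 on the standardised scale) instead of standardising after the large generated interaction.
3. Generate the moderator as it will be measured: one value per participant if it is a baseline score.
4. Set the seed directly before the Aim 2 data are drawn, or average over several generated datasets, because the result varies by dataset.
5. Restate the Aim 2 power for the 5-df interaction, with the coefficients in residual-SD units, and note that the likelihood-ratio test is slightly liberal at this sample size.
6. Optionally, say which experimental condition each level of x represents.

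The cost is a few lines of code and a restated figure, possibly somewhat below .91. Nothing here calls for more participants.
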